11.2 Exclusion Criteria

A subject will be excluded from participation in the study if he or she meets any of the following exclusion criteria at Screening and/or Baseline:

1. Subject has an invasive fungal disease with central nervous system involvement unless the subject is planned to receive combination therapy with ibrexafungerp and other antifungal.
2. Subject has an inappropriately controlled fungal disease source (e.g., persistent catheters, devices, identified undrained abscess) that is likely to be the source of the fungal disease.
3. Subject is hemodynamically unstable and/or requiring vasopressor medication for blood pressure support.
4. Subject has abnormal liver test parameters: AST or ALT $>10 \times$ ULN and/or total bilirubin $>5 \times$ ULN.

Note: Subjects with unconjugated hyperbilirubinemia with a diagnosis of Gilbert's disease **are not excluded.**

5. Subject is unlikely to survive 30 days.
6. Subject has any other condition or laboratory abnormality that, in the judgment of the Investigator, would put the subject at unacceptable risk for participation in the study or may interfere with the assessments included in the study.
7. Subject requires treatment with the prohibited medications.
8. Subject has known hypersensitivity to ibrexafungerp.
9. Subject is pregnant or lactating.
10. Subject has received any other investigational drug (i.e., new chemical entity) within at least 30 days (or 5 and a half half-lives of the investigational product) before signing the ICF.
11. Subject is an employee of SCYNEXIS, Inc., the Investigator, or contract research organization involved in the study, or an immediate family member (partner, offspring, parents, siblings, or sibling's offspring) of an employee involved in the study.

12. Subject or legal representative is/are unable to provide written informed consent for any reason.
13. Subject is unlikely to comply with protocol requirements.

11.3 Discontinuation Criteria

A subject may be discontinued from the study or study drug for any of the following reasons:

- Withdrawal of consent by the subject and/or subject's legal guardian;
- Investigator or Sponsor decision that withdrawal is in the subject's best interest;
- Deterioration of the clinical condition or delayed response requiring, in opinion of the Investigator, alternative therapy;
- Occurrence of an AE that, in the opinion of the Investigator, warrants discontinuation of the subject from the study drug;
- Pregnancy;
- Lost to follow up (every attempt should be made to contact the subject).

The reason for a subject's discontinuation of treatment or withdrawal from the study will be clearly documented in the source documents and on the electronic case report form (eCRF).

For VVC subjects, all TOC procedures should be performed for subjects who discontinue from the study before the TOC visit, and all 25-Day FU procedures should be performed for subjects who discontinue from the study after the TOC visit but before the 25-Day FU visit.

For all other fungal diseases, at the time of discontinuation, all EOT procedures should be performed for subjects who discontinue from treatment on or before the EOT visit and the 6-Week FU visit should also be completed. All 6-Week FU procedures should be performed for subjects who discontinue from the study after the EOT visit and on or before the 6-Week FU visit. All follow up visits should be completed for discontinued subjects regardless of need for additional antifungal therapy.

11.4 Replacement of Discontinued Subjects

Subjects who discontinue early from randomized treatment will not be replaced.

12.0 Study Treatments

12.1 Study Treatment Groups

This is an open-label, non-comparator, single-arm study. All subjects will receive ibrexafungerp monotherapy except subjects with refractory or relapsing invasive pulmonary aspergillosis (IPA), who will receive combination therapy. Combination therapy may also be administered to other

subjects based on Investigator's judgement and contingent on Sponsor approval. Subjects will receive ibrexafungerp on an inpatient or outpatient basis, as needed for each fungal disease.

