Subjects will be evaluated for safety throughout the study, including parameters such as physical exam, vital signs, adverse events (AEs) and concomitant medications, and safety laboratory tests (hematology, blood chemistry and urinalysis).

Results from the study will be analyzed against historical and concurrent SOC-treated subjects, who will be selected from literature reviews and other data resources.

Target Population: Male and female subjects ≥ 18 years of age with documented eligible severe fungal diseases for whom SOC antifungal treatment is not appropriate due to refractoriness, resistance, intolerance, relapse, toxicities, need for oral therapy or other reasons.

KEY Inclusion Criteria:

Subject must fulfill all of the following **KEY** criteria at Screening and/or Baseline to be eligible for study admission:

1. Subject is a male or female adult ≥ 18 years of age on the day the study informed consent form (ICF) is signed.
2. Subject has a documented eligible fungal disease that has been refractory or resistant to SOC, has relapsed after, or the subject has intolerance to or demonstrated toxicities resulting from an approved SOC antifungal treatment. The subject is also eligible if, in the judgement of the Investigator, long-term IV antifungal therapy is not feasible or desirable due to clinical (isolate is resistant to or has a high MIC and is unlikely to respond to antifungal SOC) or logistical circumstances or if other antifungal alternatives are not appropriate.

A summary of eligible fungal diseases is listed below and a detailed description of diagnostic, refractoriness, intolerance, toxicity and relapse criteria is available in [Table 5](#) in the full protocol:

- Acute or chronic invasive candidiasis, including candidemia
- Acute or chronic severe mucocutaneous candidiasis, including:
 - Esophageal candidiasis (EC)
 - Oropharyngeal candidiasis (OPC)
 - Chronic mucocutaneous candidiasis (CMC)
 - Vulvovaginal candidiasis (VVC)
- Disseminated/invasive dimorphic fungi:
 - Coccidioidomycosis
 - Histoplasmosis
 - Blastomycosis
- Chronic Pulmonary Aspergillosis (CPA)
- Allergic Bronchopulmonary Aspergillosis (ABPA)
- Invasive Pulmonary Aspergillosis (IPA)
- Other emerging fungi including yeasts and molds (e.g., sachromycetes, scopulariopsis, mucorales)

KEY Exclusion Criteria:

Subject will be excluded from participation in the study if he/she meets any of the following **KEY** exclusion criteria at Screening and/or Baseline:

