1. Subject has an invasive fungal disease with central nervous system involvement unless the subject is planned to receive combination therapy with ibrexafungerp and other antifungal.
2. Subject has an inappropriately controlled fungal disease source (e.g., persistent catheters, devices, identified undrained abscess) that is likely to be the source of the fungal disease.
3. Subject is hemodynamically unstable and/or requiring vasopressor medication for blood pressure support.
4. Subject has abnormal liver test parameters: AST or ALT >10 x ULN and/or total bilirubin >5 x ULN.
Note: Subjects with unconjugated hyperbilirubinemia with a diagnosis of Gilbert's disease **are not excluded.**
5. Subject is unlikely to survive 30 days.

Study Drugs:

Ibrexafungerp citrate drug product for oral administration will be supplied as compressed oral tablets containing 250 mg of ibrexafungerp active ingredient on a free base basis. In addition to the active ingredient, the oral tablet formulation also contains silicified microcrystalline cellulose, crospovidone, mannitol, colloidal silicon dioxide, magnesium stearate (non-bovine), and butylated hydroxyanisole. Ibrexafungerp is packaged in bottles containing 30 tablets.

Ibrexafungerp tablets are to be stored at room temperature: between 15°C and 25°C with allowable limited excursions of up to 30°C.

Randomized Treatment Groups: This is an open-label, non-comparator, single-arm study. All subjects will receive ibrexafungerp monotherapy except subjects with refractory or relapsing invasive pulmonary aspergillosis (IPA), mucormycosis or other molds with unpredictable ibrexafungerp activity, who will receive combination therapy. Combination therapy may also be administered to other subjects based on Investigator's judgement and contingent on Sponsor approval. Subjects will receive ibrexafungerp on an inpatient or outpatient basis, as needed for each fungal disease.

Ibrexafungerp Monotherapy for All fungal Diseases, Excluding VVC

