Subjects will receive ibrexafungerp monotherapy given as an initial loading dose of 750 mg (3 tablets of 250 mg each) given BID (total daily dose = 1500 mg) during the first 2 days of treatment and then subsequent oral doses of 750 mg (3 tablets of 250 mg each) QD for up to 180 days, depending on fungal disease. Treatment beyond 180 days may be permitted under certain circumstances to be agreed upon by the Investigator and the Sponsor on a per-subject basis. Subjects may be considered for re-enrollment upon discussion with the sponsor.

If subjects cannot swallow the whole tablet, the tablets may be split. In the event subjects experience gastrointestinal intolerance on the 750 mg QD dose, the tablets may be split and/or administered at 10 to 20-minute intervals. [REDACTED]

Ibrexafungerp Monotherapy for VVC

Subjects with VVC will receive ibrexafungerp monotherapy given as oral doses of [REDACTED] Subjects treated for VVC who have a recurrence may receive additional cycles of ibrexafungerp treatment similar to the initial regimen upon discussion with the Sponsor.

Ibrexafungerp Combination Therapy

Monotherapy with ibrexafungerp is not recommended for refractory or relapsing IPA or mucormycosis. All subjects enrolled for refractory or relapsing IPA or mucormycosis should receive ibrexafungerp given

as combination therapy. Subjects with IPA and intolerance to other SOC options can be considered for enrollment to receive ibrexafungerp monotherapy, upon discussion with the Sponsor.

For subjects who have infections due to other emerging fungi, including yeasts and molds, but have no culture isolate available (to confirm susceptibility to ibrexafungerp), combination therapy should be considered and discussed with the Sponsor. Combination therapy will also be allowed for other subjects based on Investigator's judgement and contingent on Sponsor approval.

Acceptable antifungal therapy includes voriconazole, isavuconazole, posaconazole, or amphotericin B (AMB) at the doses recommended per their label. When used in combination with the azoles, the dose of ibrexafungerp should be reduced from 750 mg to 500 mg.

The following combination options are allowed:

- addition of ibrexafungerp to any ongoing antifungal therapy
- replacement of one (toxic/ineffective) element of a two-antifungal combination therapy with ibrexafungerp
- replacement of current monotherapy with a new combination, generally:

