Screening ^a (Days -1 [-3])	Day 1 ^a (Baseline) & Day 2	Day 3 to EOT	EOT or Day 84 (CMC) EOT or Day 90 (CPA and ABPA) whichever comes first	Last dose of study drug (up to 180 days from Day 1)	6 weeks (\pm 7 days) after EOT	3 and 6 months after EOT for ABPA subjects only

Abbreviations: ABPA = allergic bronchopulmonary aspergillosis; CMC = chronic mucocutaneous candidiasis; CPA = chronic pulmonary aspergillosis; EOT = end of treatment; TOC = test of cure

a: Screening and Baseline (Day 1) may occur on the same day.

Subjects with VVC will have a Screening visit, a Baseline/Day 1 visit, and scheduled visits on [REDACTED] 25-day FU (Day 32) and 35-day FU (Day 42). VVC subjects will receive treatment [REDACTED]

The EOT and 35-Day FU visits may be a phone contact for asymptomatic subjects. A summary of the overall treatment and follow-up schedule for VVC subjects is provided in [Table 4](#).

Table 4 Summary of Overall Treatment and Follow-Up Schedule for VVC Subjects

Pre-study Activities	Ibrexafungerp Dosing	EOT (Phone/on site)	TOC	25-Day FU	35-Day FU (Phone/on site)
Screening ^a (Day -1)	[REDACTED]	[REDACTED]	Day 17 (\pm 3)	Day 32 (25 days after EOT; 32 days after first dose)	Day 42 (35 days after EOT; 42 days after first dose)

Abbreviations: EOT = end of treatment; FU = follow up; TOC = test of cure; VVC = vulvovaginal candidiasis

a: Screening and Baseline (Day 1) may occur on the same day.

Study Treatments

Eligible subjects (excluding VVC subjects) will receive ibrexafungerp monotherapy given as an initial loading dose of 750 mg BID during the first two days of treatment (Day 1 and Day 2) and then subsequent oral doses of 750 mg QD for up to 180 days depending on fungal disease. Ibrexafungerp given as combination therapy will be required for all subjects with refractory or relapsing IPA, mucormycosis and other molds with unpredictable ibrexafungerp activity based on Investigator's judgement and contingent on Sponsor approval. The treatment duration may be extended beyond 180 days, if needed, for certain fungal diseases. Sponsor approval must be obtained for any extension of treatment beyond 180 days. For subjects receiving extended treatment, a 4-week visit schedule may be followed. Subjects who have a recurrence after EOT may also be considered for re enrollment upon discussion with the sponsor. Subjects who are re

enrolled will follow the protocol defined visit schedule.

Subjects with VVC will receive oral doses of [REDACTED]

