12.1.3 Ibrexafungerp Combination Therapy

Monotherapy with ibrexafungerp is not recommended for refractory or relapsing IPA. All subjects enrolled for refractory or relapsing IPA, mucormycosis or other molds with unpredictable ibrexafungerp activity should receive ibrexafungerp given as combination therapy. Subjects with IPA and intolerance to other SOC options can be considered for enrollment to receive ibrexafungerp monotherapy, upon discussion with the Sponsor.

For subjects who have infections due to other emerging fungi, including yeasts and molds, but have no culture isolate available (to confirm susceptibility to ibrexafungerp), combination therapy should be considered and discussed with the Sponsor. Combination therapy will also be allowed for other subjects based on Investigator's judgement and contingent on Sponsor approval.

Acceptable antifungal therapy includes voriconazole, isavuconazole, posaconazole, fluconazole or amphotericin B (AMB) at the doses recommended per their label. When used in combination with the azoles, the dose of ibrexafungerp should be reduced from 750 mg to 500 mg.

Table 8 Ibrexafungerp – Azole Combination Therapy Dosing Regimen

	Treatment Days	Additional Antifungal	+	Ibrexafungerp Dosing Regimen	Total Ibrexafungerp Daily Dose
Loading Dose	Study Days 1 and 2	Per label	+	500 mg BID: 500 mg (2 tablets x 250 mg) AM 500 mg (2 tablets x 250 mg) PM	1000 mg
Maintenance Dose	Study Day 3 to EOT	Per label	+	500 mg QD: 500 mg (2 tablets x 250 mg)	500 mg

Abbreviations: AM = morning; EOT = end of treatment; PM = evening; QD = once a day

The following combination options are allowed:

- addition of ibrexafungerp to any ongoing antifungal therapy
- replacement of one (toxic/ineffective) element of a two-antifungal combination therapy with ibrexafungerp

- replacement of current monotherapy with a new combination, generally:
 - replacement of AMB monotherapy with an azole plus ibrexafungerp combination, or
 - replacement of an azole monotherapy with an AMB plus ibrexafungerp combination
- continuation of an azole plus echinocandin combination where the subject could go home on an oral regimen by replacing the parenteral echinocandin with ibrexafungerp

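### The opening paragraph of Protocol 12.1 mandates combination therapy only for refractory or relapsing IPA, in conflict with the synopsis, 10.1, 12.1.3 and SAP 2.3 on mucormycosis and other unpredictable molds

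*Protocol*

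**What the plan says.** The opening paragraph of Protocol 12.1 (Study Treatment Groups) states: "All subjects will receive ibrexafungerp monotherapy except subjects with refractory or relapsing invasive pulmonary aspergillosis (IPA), who will receive combination therapy". It goes on: "Combination therapy may also be administered to other" subjects, subject to the Investigator's judgement and the Sponsor's approval.

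The synopsis paragraph on treatment groups uses almost the same sentence with a longer exception: "except subjects with refractory or relapsing invasive pulmonary aspergillosis (IPA), mucormycosis or other molds with unpredictable ibrexafungerp activity, who will receive combination therapy". Its later paragraph on combination therapy says "Monotherapy with ibrexafungerp is not recommended for refractory or relapsing IPA or mucormycosis", followed by "All subjects enrolled for refractory or relapsing IPA or mucormycosis should receive ibrexafungerp given" as combination therapy.

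Protocol 10.1 says that combination will be required for refractory or relapsing IPA, "mucormycosis and other molds with unpredictable ibrexafungerp activity based on Investigator's judgement and contingent on Sponsor approval". SAP 2.3 repeats that sentence.

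Subsection 12.1.3, which also holds the combination dose table and the permitted combinations, says: "All subjects enrolled for refractory or relapsing IPA, mucormycosis or other molds with unpredictable ibrexafungerp activity should receive ibrexafungerp given as combination therapy". Its preceding sentence, on where monotherapy is not recommended, names refractory or relapsing IPA alone.

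The synopsis lists among the eligible diseases "Other emerging fungi including yeasts and molds (e.g., sachromycetes, scopulariopsis, mucorales").

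**The concern.** The first sentence of 12.1 is exhaustive in form: everyone gets monotherapy unless they fall in the named exception. It therefore cannot be read as silent on mucormycosis or the other molds. It puts them on monotherapy, with combination as an option. Four other places direct combination for the same subjects, and one of those is a subsection of 12.1 itself.

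This is an instruction on what treatment to give. A site that relied on the opening paragraph could treat mucormycosis with ibrexafungerp alone, which the synopsis advises against. The dose can change too: 12.1.3 lowers each ibrexafungerp dose from 750 mg to 500 mg when the partner is an azole. It is also unclear whether monotherapy in such a subject is a protocol deviation. It complies with the opening of 12.1 and departs from 12.1.3.

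**Working it through.** No arithmetic is involved beyond a count. The inputs are the current general statements of the combination rule. The amendment history and the disease-specific rows of Protocol Table 5 are left out.

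| Place | Refractory or relapsing IPA | Mucormycosis | Other unpredictable molds | Strength |
|---|---|---|---|---|
| Synopsis, treatment groups | yes | yes | yes | will |
| Synopsis, combination therapy | yes | yes | not named | should |
| Protocol 10.1 | yes | yes | yes | required, with a qualifier |
| Protocol 12.1, opening paragraph | yes | **no** (optional) | **no** (optional) | will, for IPA only |
| Protocol 12.1.3 | yes | yes | yes | should |
| SAP 2.3 | yes | yes | yes | required, with a qualifier |

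Step 1. Combination is directed for mucormycosis in 5 of 6 statements and for the other molds in 4 of 6. The opening of 12.1 is the only one that directs it for neither.

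Step 2. The verbs differ. *Will* and *required* are firmer than *should*, so the five statements are not equally strong. All five still point towards combination, whereas 12.1 points towards monotherapy. The conflict does not depend on treating the verbs as equal.

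Step 3. This is not a summary that abbreviates a fuller body text. The synopsis has the longer exception, and the body section named for treatment groups has the shorter one.

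Step 4. Two smaller mismatches appear in the same comparison. The sentence in 12.1.3 advising against monotherapy omits mucormycosis, while the matching synopsis sentence includes it. The synopsis sentence on who should receive combination omits the other molds, while the matching sentence in 12.1.3 includes them.

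Step 5. Effect on the analysis. Protocol 18.4.3 presents data by whether combination was received, so that split follows actual treatment, whichever text governs. The two per-protocol exclusions listed in SAP 7 concern unapproved additional antifungals and a late EOT visit. Neither addresses monotherapy given where combination was directed.

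**The case against.** The best defence is that 12.1.3 lies within 12.1, is the section devoted to combination therapy, and names all three groups. The opening paragraph is then an incomplete overview, and it does not forbid combination in mold subjects. Protocol 10.1 and 14.1.2 also require the Sponsor to approve each subject, so a wrong regimen would probably be caught. This stands, and it is why the risk is limited. It does not remove the conflict, because Sponsor approval does not say which sentence the person approving should apply.

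A second objection concerns eligibility. The row of Table 5 for other emerging fungi does not name Mucorales. It asks for general in vitro susceptibility or an ibrexafungerp MIC of at most 4 ug/mL, and it asks only that combination be considered when no isolate is available. That is a fair caution about how many such subjects enrol. It does not make the group empty: the synopsis lists Mucorales as eligible, and 10.1 and 12.1.3 give rules for subjects with mucormycosis.

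A reader might infer two stronger claims, and the documents support neither. The first is that the protocol as a whole permits monotherapy in mucormycosis. Only the opening paragraph of 12.1 does so when read alone. The second is that the closing qualifier in 10.1 and SAP 2.3, on Investigator judgement and Sponsor approval, turns the requirement into an option and should be deleted. It can equally mean that the Investigator judges which molds count as unpredictable. The documents do not define that term, and the qualifier is the only text that could say who decides. Removing it could leave a mandatory group with neither a definition nor a decision-maker.

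**Conclusion.** The conflict is real and narrow. As written, the opening paragraph of Protocol 12.1 gives the wrong default for mucormycosis and other unpredictable molds, against the synopsis, 10.1, 12.1.3 and SAP 2.3. For mucormycosis it also conflicts with the synopsis paragraph on combination therapy. It should be corrected because it governs treatment and the correction costs almost nothing. It is not a critical flaw: the specific rule in 12.1.3 is right, and every subject needs Sponsor approval before study drug.

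The size cannot be put as a number of subjects, because the documents give none. No endpoint definition, sample size, alpha or power figure changes. The conclusion assumes that the fuller rule is the intended one, which its appearance in four separate places makes very likely.

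**What to change.** 1. Protocol 12.1, opening paragraph: replace the exception with the synopsis wording, "except subjects with refractory or relapsing invasive pulmonary aspergillosis (IPA), mucormycosis or other molds with unpredictable ibrexafungerp activity, who will receive combination therapy". Leave the sentence on optional combination for other subjects as it is.
2. Protocol 12.1.3, sentence advising against monotherapy: add mucormycosis after IPA, so that it agrees with the synopsis.
3. Synopsis, combination therapy paragraph, sentence on who should receive combination: add the other molds of unpredictable activity, so that it agrees with 12.1.3.

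Leave 10.1 and SAP 2.3 unchanged.

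The cost is three wording edits in the protocol and none in the SAP. Eligibility, procedures, data collection and analyses stay the same, and subjects already treated under 12.1.3 are unaffected. If enrolment has closed, the sponsor can instead record that 12.1.3 governs in the significant protocol deviations rules document described in SAP 4.2, before database lock.
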